### Study Intervention

At UCLA Health, cataract surgery planning is initiated when a patient is evaluated by a UCLA ophthalmologist and deemed an appropriate candidate for the procedure. The patient is then asked to make an appointment for a pre-op visit with their primary care provider (PCP), cardiologist or another UCLA physician. The Centres for Medicare and Medicaid Services and the Joint Commission require that a pre-op visit be completed within 30 days of the surgery.

At this pre-op appointment, the provider completes a required history and physical, sometimes working off a checklist provided by the surgeon that may include a list of suggested tests such as EKG, cardiac stress test, Complete Blood Count (CBC), electrolytes and CXR. The ordering of these tests is left to the discretion of the physician completing the pre-op evaluation. The decision to order tests and procedures is influenced by the provider's previous experiences, preferences and interpretation of the guidelines.

The intervention will deploy one of the EHR nudge alerts (control, nudge 1, nudge 2 or nudge 3) such that each physician in the study will only get one of the nudges (or none of them) for the duration of the study. These alerts will be triggered when a physician begins to order a pre-op test for patients during their pre-op visit. The full list of pre-op tests, informed by Chen et al and Steinberg et al, was identified using Current Procedural Terminology codes. These tests fall into several categories including chemistry panel, complete blood count, coagulation panel, urinalysis, EKG, cardiac stress test, CXR and pulmonary function tests. The full list of pre-op tests can be found in the Appendix. Details of the nudge alert including opt-out features are described below.

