### Three Intervention Arms

Nudge 1 will display as 'UCLA Ophthalmologists and Anesthesiologists ADVISE AGAINST routine pre-op tests, which do not increase the patient's safety and are considered inappropriate per current evidence-based recommendations (see UCLA Ophthalmology, UCLA Anesthesiology, ASA and AAO recommendations). The UCLA Pre-op Eval and Planning Center (PEPC) will order any necessary day of surgery labs'.

Nudge 2 will display as 'UCLA Ophthalmologists and Anesthesiologists ADVISE AGAINST routine pre-op tests, which can increase the patient's out-of-pocket costs and are considered inappropriate per current

evidence-based recommendations (see UCLA Ophthalmology, UCLA Anesthesiology, ASA and AAO recommendations). The UCLA PEPC will order any necessary day of surgery labs'.

Nudge 3 (figure 3) will display as 'UCLA Ophthalmologists and Anesthesiologists ADVISE AGAINST routine pre-operative tests, which can cause aggravation and psychological stress for the patient and are considered inappropriate per current evidence-based recommendations (see UCLA Ophthalmology, UCLA Anesthesiology, ASA, and AAO recommendations). The UCLA Pre-op Eval and Planning Center (PEPC) will order any necessary day of surgery labs'.

We designed these alerts to minimise the burden on physicians while also including a hard stop, so that if a physician chooses to order a pre-op test, they will need to type an explanation. This behavioural intervention is known as 'accountable justification', which has been shown effective in reducing low-value care. Specifically, as part of the alerts, physicians can remove the order with a single click on 'Accept'. If they choose not to remove the order, they can click 'Keep' and will be required to click on the 'Explain' button and provide free text stating why they continued with placing the order after exposure to the nudge

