### Data collection methods

All data will be collected from the UCLA Health EPIC EHR 'CareConnect' and from surveys administered to providers. This data will be stored securely and only accessible to research personnel trained in confidentiality and privacy procedures. An independent Data Safety Monitoring Board will provide ongoing oversight and data audits. To compare the cost of pre-op testing among study arms, we will use publicly available Medicare payment rates and UCLA Health commercial payment rates.

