### Primary and secondary outcome analysis

We will measure and compare rates of testing in the 12 months before and 12 months after initiation of the randomisation (primary outcome) to determine whether the EHR-based intervention is successful in changing physician behaviour. We will also compare each of the three intervention arms and the usual care arm and will perform exploratory comparisons between nudge 1, nudge 2 and nudge 3 (secondary outcome) to determine whether certain behavioural economic framing techniques are more effective than others at reducing pre-op testing.

Other secondary outcomes will include the percentage of patients who received specific categories of pre-op tests including labs, EKGs and CXRs, same-day surgery cancellations and physician-level

experience measured by the surveys. We will also estimate cost savings associated with the intervention (described below). Evaluation of the primary and secondary outcomes will be performed using generalised linear mixed-effects models at the patient level. We will investigate the impact of all nudges versus control, which will require a threefold correction. As a secondary analysis, we will conduct pairwise comparisons of the nudges. Models will include fixed nudge 1, nudge 2 and Nudge 3 effects, a fixed study period effect (postnudge intervention vs prenudge intervention), second-order interactions between these effects, a fixed stratum effect (hospitalist vs PCP) and random physician effects. Physician effects will account for clustering of patients by physician. Comparisons between changes in utilisation rates across study arms will be estimated and tested using model contrasts. All pairwise comparisons of changes between study arms will be performed to identify the most effective nudge, and Bonferroni corrections will be applied to control the familywise type I error rate at 5%. Intervention effects will be summarised using ORs, 95% CIs and p values (with multiple comparison corrections). Differences between strata will be similarly summarised.

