### Power

Preliminary analyses of UCLA Health data show that the baseline rate of testing is 65%. In a prior quality improvement study conducted at a different health system, we reduced pre-op lab testing by 59% (a reduction from 90% to 31%). We conservatively estimate an effect half as large (30%) in each intervention arm.

To calculate savings from reduced use of medical services, we will multiply the estimates of utilisation (ie, quantity) for each of the pre-op services measured by the relevant payment rates for the services based on the coverage type for the patient (ie, Medicare and average commercial payment rates per service). We will then compare differences in spending overall and by specific services (ie, lab testing, EKGs) between the control arm and each of the intervention arms and a pooled estimate of the three-nudge intervention arms. We will disaggregate the savings to measure the amount and proportion accrued by the health system/payer versus the patient. An extension of this analysis will estimate how reducing the utilisation of pre-op testing affect different parties; we will disaggregate the savings estimates by type of payer contract (ie, capitated vs fee-for-service(FFS)) to derive estimates of savings to the health systems versus the payer. Under capitated payments, the savings accrue to the health system, while under FFS payments, the savings accrue to the payer and represent revenue losses for the health system.

We will extrapolate observed saving estimates to compute savings the Medicare FFS programme might expect to accrue if similar reductions in the utilisation of pre-op services for cataract surgery were observed in the Medicare population. To generate these savings estimates, we will compute the number of Medicare patients undergoing cataract surgery in a single year and the fraction of patients who have these pre-op tests. We will then take our estimates of reduction in utilisation and apply these estimates to the current use of pre-op testing utilisation in the Medicare FFS programme to determine the number

of services that would be reduced. We would then apply FFS payment rates to the number of services that would be reduced to estimate savings to Medicare. Finally, we will develop estimates of longer term savings in a year–year time range, applying a discount rate to costs, assuming that the observed reduced amount of services used remained similar after the 1-year study period ended.

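### Savings are priced from pre-op services alone, so tests that the nudges only move to a later date could be booked as saved

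*Combined protocol and SAP*

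**What the plan says.** In the SAP, Primary and secondary outcome analysis announces the estimate: "We will also estimate cost savings associated with the intervention (described below". The method appears under the Power heading: "we will multiply the estimates of utilisation (ie, quantity) for each of the pre-op services measured by the relevant payment rates", with rates chosen by the patient's coverage. Data collection methods sets the same scope: "To compare the cost of pre-op testing among study arms, we will use publicly available Medicare payment rates and UCLA Health commercial payment rates". The contrast is then defined: "We will then compare differences in spending overall and by specific services (ie, lab testing, EKGs) between the control arm" and each nudge arm, and also the three nudge arms pooled. Two projections follow, one to the Medicare fee-for-service programme and one over several years with discounting. Both carry forward the trial's reduction in utilisation.

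Four other statements bear on what that quantity captures.

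- Study Intervention, on when the alert acts: "These alerts will be triggered when a physician begins to order a pre-op test for patients during their pre-op visit".
- Study Intervention, on who holds the visit: "The patient is then asked to make an appointment for a pre-op visit with their primary care provider (PCP), cardiologist or another UCLA physician".
- Three Intervention Arms: each alert refers labs onward, in nudges 1 and 3 with the words "The UCLA Pre-op Eval and Planning Center (PEPC) will order any necessary day of surgery labs" and in nudge 2 with the centre's name abbreviated. Under Control Arm, usual-care physicians see no alert and so do not get this message.
- The secondary outcomes are listed as "including labs, EKGs and CXRs, same-day surgery cancellations and physician-level" experience, so cancellations are measured. No section gives them a cost.

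No section sets a per-patient window for counting tests, or says whether tests ordered for the day of surgery are among the services measured.

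**The concern.** A saving from less testing is real only if the test is not done at another time. The alert acts at one moment, the pre-op visit. The physician there may also look after the patient in the longer term, and the alert itself points to another team for labs. Either route could move a chemistry panel, blood count or EKG rather than remove it (the referral in the alert covers labs only). A formula that counts pre-op services alone cannot tell a moved test from an avoided one. Because control physicians get no alert, displacement caused by the alert would differ by arm and would not cancel in the contrast.

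At stake are the by-arm and pooled savings, the payer split and both projections. A payer who pays for the same test later has saved nothing. Under capitation the same is true of the health system.

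Cancellations raise a smaller, related question. The plan measures them but the health-system savings cannot respond to them.

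**Working it through.** **The plan's own figures.** The documents state no savings amount, payment rate, cancellation rate or postponed share, so there is no savings figure to reproduce. The nearest figure is the assumed effect under Power: 90% − 31% = 59 points, half of which is 29.5, stated as 30%. The text does not say whether 30% means points or a relative reduction. From the 65% baseline, these are a fall of 30 points (to 35%) or of 0.30 × 65 = 19.5 points (to 45.5%). Both are carried below.

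**Displacement.** Let D be the fall in testing at the pre-op visit, c the payment per test, and f the share of that fall made up later, net of later testing in the control arm. Assume later tests cost the same on average as those dropped.

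- Plan: saving = D × c
- Net: saving = D × (1 − f) × c
- Overstatement = 1/(1 − f) − 1, whatever D is

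For scale, Inclusion Criteria gives 1122 visits in 2019. With four equal arms, 1122 × 3/4 = 841.5 nudged visits a year. Fewer tested visits: 841.5 × 0.30 = 252, or 841.5 × 0.195 = 164.

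| f (assumed) | Overstatement | Not saved, of 252 | Not saved, of 164 |
|---|---|---|---|
| 0 | 0% | 0 | 0 |
| 10% | 11% | 25 | 16 |
| 20% | 25% | 50 | 33 |
| 30% | 43% | 76 | 49 |
| 50% | 100% | 126 | 82 |

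For the day-of-surgery route, f is zero if those tests are already in the count.

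**Cancellations.** Let dC be the nudge-minus-control difference in same-day cancellations and K the cost of one. With f = 0, net saving = D × c − dC × K, which reaches zero at dC = D/(K/c). The ratio K/c is assumed.

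| K/c (assumed) | Break-even rise, D = 30 points | Break-even rise, D = 19.5 points |
|---|---|---|
| 5 | 6.0 points | 3.9 points |
| 10 | 3.0 points | 1.95 points |
| 20 | 1.5 points | 0.98 points |

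The sign can go the other way. With D = 30 points, K/c = 10 and cancellations falling by 1 point, the plan counts 30 payment units per 100 patients where the net is 30 + 10 = 40. These lines treat the whole saving as belonging to the party that bears the cancellation cost. The plan's own payer split shows that this is a simplification.

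**Checks on a longer window.** The 1122 visits came from 995 patients, so 1122 − 995 = 127 visits (11%) were repeats. A window that runs past the next pre-op visit would count some tests twice. Windows opened in the pre-intervention year also spill over. At 120 days, for example, with even accrual, 120/365 = 33% of them would run into the nudge period.

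**The case against.** The strongest reply is that the scope is disclosed: the plan says that it costs pre-op testing, and it reports cancellations as a separate outcome. On that view, a wider net-cost measure is a matter of preference. This has force for cancellations. It has less for displaced tests, because the plan presents the result as savings from the intervention, splits it by payer and projects it to Medicare. Those uses need tests that are not done, and not merely tests done later.

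A reader might also infer more than the documents support.

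- *That the savings are biased upward.* This is conditional. It needs tests to be displaced and left uncounted, or cancellations to rise. Nothing in the documents shows either. Falling cancellations, or uncosted follow-up care prompted by test results, would push the other way.
- *That day-of-surgery tests are left out.* The plan is silent. Its outcome by test category concerns what patients received, with no limit on who ordered it, and could include them. The defect here is an undefined window.
- *That dropped tests will be re-ordered by the patient's regular physician.* The plan lists who may hold the visit but gives no frequencies and does not mention re-ordering. The route is plausible, not documented.
- *That cancellations distort the Medicare projection.* That projection is services reduced times payment rates. A health system's cost for a lost slot does not enter it.
- *That cancellation costs should simply be deducted from the total.* The plan notes that fee-for-service savings go to the payer and are lost revenue to the health system. A deduction from undivided savings would describe no party's position, and pooling the arms could hide one nudge that raises cancellations.

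**Conclusion.** The point holds in a limited form. The savings quantity covers pre-op services only, and both projections inherit it. A listed test done after surgery would count as saved, and so would a day-of-surgery test if those are not counted. Savings can be overstated if the nudges displace tests. The illustrative 11% to 43% rests on assumed displaced shares of 10% to 30% and equal prices. The true figure could be zero, and the net direction of all omitted items is unknown. The cancellation figures likewise rest on assumed cost ratios and bear only on the health-system view. The primary testing comparison is not in question.

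**What to change.** Amend the savings paragraphs under Power as follows.

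1. Keep the pre-op-only estimate and label it gross savings.
2. Report beside it a net figure that counts all tests on the same CPT list from the pre-op visit, through the day of surgery, to a fixed follow-up point stated in advance, in any encounter and by any ordering clinician. This also settles whether day-of-surgery tests count.
3. Compare the net figure between the randomised arms in the post-randomisation period only. End each window at the patient's next cataract pre-op visit so that no test is counted twice.
4. Show the Medicare fee-for-service and multi-year projections on both the gross and the net basis.
5. Report same-day cancellations by arm next to the health-system savings. As a sensitivity analysis only, add the break-even cost per cancellation (the arm's health-system saving per patient divided by its difference in cancellation rate from control) with its interval. State that no break-even exists where cancellations do not rise, and that the interval is unbounded where that difference could be zero. Do not apply this to the Medicare projection.

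The cost is SAP wording and a longer EHR extract, with no participant contact. The plan already extracts cardiovascular events to 30 days after surgery, so the data source is in place. Unrelated later tests add noise in every arm and widen the interval for the net figure. If later tests vary as much as pre-op tests and independently of them, the widening is √2 = 1.41, or about 40%. The net saving may also be smaller than the gross one.
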